4.2. Extent of Study Drug Exposure and Adherence

Extent of exposure to study drug will be examined by assessing the total duration of exposure to study drug and the level of adherence relative to the study drug regimen specified in the protocol by component (andecaliximab/nivolumab).

4.2.1. Duration of Exposure to Study Drug

Total duration of exposure to study drug will be defined as last dosing date minus first dosing date plus 14, regardless of any temporary interruptions in study drug administration, and will be expressed in weeks using up to 1 decimal place (eg, 4.5 weeks). If the last study drug dosing date is missing, the latest date among the study drug end date, clinical visit date, laboratory sample collection date, and vital signs assessment date that occurred during the on-treatment period will be used for subjects included in the final analyses.

The total duration of exposure to study drug will be summarized using descriptive statistics. Summaries will be provided by treatment group for the Safety Analysis Set.

4.2.2. Adherence to Study Drug

The total number of doses administered will be summarized using descriptive statistics.

4.2.2.1. On-Treatment Adherence

The level of on-treatment adherence to the study drug regimen will be determined by the total amount of study drug administered relative to the total amount of study drug expected to be administered during a subject's actual on-treatment period based on the study drug regimen. Investigator-prescribed interruption, reductions and escalations as specified in the protocol will be taken into account.

The level of on-treatment adherence will be expressed as a percentage using the following formula:

$$\text{On-Treatment Adherence (\%)} = \left(\frac{\text{Total Amount of Study Drug Administered}}{\text{Study Drug Expected to be Administered on Treatment}} \right) \times 100$$

Descriptive statistics for the level of on-treatment adherence with the number and percentage of subjects belonging to adherence categories (e.g., {< 75%, ≥ 75 to < 90%, ≥ 90%}) will be provided by treatment group for the Safety Analysis Set.

No formal statistical testing is planned.

A by-subject listing of study drug administration will be provided by subject ID number (in ascending order) and visit (in chronological order).

4.3. Protocol Deviations

Subjects who did not meet the eligibility criteria for study entry, but enrolled in the study will be summarized regardless of whether they were exempted by the sponsor or not. The summary will present the number and percentage of subjects who did not meet at least 1 eligibility criterion and the number of subjects who did not meet specific criteria by treatment group based on the ITT Analysis Set. A by-subject listing will be provided for those subjects who did not meet at least 1 eligibility (inclusion or exclusion) criterion. The listing will present the eligibility criterion (or criteria if more than 1 deviation) that subjects did not meet and related comments, if collected.

Protocol deviations occurring after subjects entered the study are documented during routine monitoring. The number and percentage of subjects with important protocol deviations by deviation reason (eg, nonadherence to study drug, violation of select inclusion/exclusion criteria) will be summarized by treatment group for the ITT Analysis Set. A by-subject listing will be provided for those subjects with important protocol deviation.

5. BASELINE CHARACTERISTICS

5.1. Demographics

Subject demographic variables (ie, age, sex, race, and ethnicity) and baseline characteristics (body weight [in kg], height [in cm], body mass index [BMI; in kg/m²]) will be summarized by treatment group and overall using descriptive statistics for continuous variables, and using number and percentage of subjects for categorical variables. The summary of demographic data will be provided for the ITT Analysis Set.

A by-subject demographic listing, including the informed consent date, will be provided by subject ID number in ascending order.

5.2. Other Baseline Characteristics

Other baseline characteristics include, ECOG, PD-L1 status, and MMR status at screening. These baseline characteristics will be summarized by treatment group and overall using descriptive statistics for continuous variables and using number and percentage of subjects for categorical variables. The summary of baseline characteristics will be provided for the ITT Analysis Set. No formal statistical testing is planned.

A by-subject listing of other baseline characteristics will be provided by subject ID number in ascending order.

5.3. Medical History

General medical history data will be collected at screening and listed only. General medical history data will not be coded.

A by-subject listing of general medical history will be provided by subject ID number in ascending order.

5.3.1. Disease History

A summary of disease-specific medical history will be provided by treatment and overall for the ITT Analysis Set. No formal statistical testing is planned. Variables to be summarized include:

- Primary tumor site
- Histology of gastric cancer
- Disease stage at screening
- Differentiation at screening
- Time since diagnosis (months)

The denominator for the percentage of histology of gastric cancer is the number of subjects with gastric cancer. The denominators for the percentage of other variables are the number of subjects in the ITT analysis set corresponding to that column.

A by-subject listing of disease history and surgical procedures will be provided by subject ID number in ascending order.

5.4. Chemotherapy and Radiotherapy Therapy

Prior (neoadjuvant, adjuvant, and metastatic) chemotherapy and radiotherapy will be summarized using descriptive statistics by treatment arm using ITT analysis set.

A by-subject listing of prior anticancer therapy and radiotherapy will be provided by subject ID number in ascending order. A by-subject listing of post-treatment chemotherapy will be provided by subject ID number and time in ascending order.

A by-subject listing of all radiotherapy will be provided by subject ID number and time in ascending order.

6. EFFICACY ANALYSES

Efficacy analysis will be performed based on the ITT Analysis Set. The investigator assessments will be used for analyses of efficacy endpoints.

P-values for the updated analyses of efficacy are for display purposes only, and no formal hypothesis testing will be conducted. Formal hypothesis testing had been conducted at the primary analysis per the SAP for primary analysis. Efficacy results in the CSR will be based on the primary analysis.

6.1. Primary Efficacy Endpoint

The primary efficacy endpoint of this study is objective response rate (ORR), defined as the proportion of subjects with best overall response of complete response (CR) or partial response (PR) after starting study drug but before starting any new chemotherapy or radiotherapy based on revised RECIST 1.1.

As sensitivity analysis, confirmed ORR, defined as the proportion of subjects with best overall response of confirmed CR or confirmed partial response (PR) after starting study drug but before starting any new anti-cancer therapy based on revised RECIST 1.1, will also be analyzed. The confirmatory response is required at least 4-week later after the initial CR/PR for confirmed ORR.

Overall response for each visit is derived in the following process. The rules should be applied by the order listed below.

- Response assessments occurring after new anticancer therapy (including radiation therapy), after missing two previous consecutive tumor scans, or after confirmed progressive disease (PD) will not be included for ORR analysis.
- If overall response for the first time point of a visit is an imaging PD, in order to differentiate “pseudo-progression (pseudo-PD)” from “definitive progression”, the first imaging PD requires confirmation either by another imaging PD at the confirmatory visit at least 4 weeks apart or by the subsequent clinical PD/ radiation therapy. The first imaging PD will be considered as “confirmed PD” by any of the following:
 - The overall response at the confirmatory visit is also PD;
 - No more tumor assessment is available that is 4 weeks apart;
 - The overall response at the confirmatory visit is non-evaluable (NE) and no more tumor assessments follow the confirmatory visit;
 - First imaging PD is followed by subsequent clinical PD or radiation therapy.

Otherwise, the first imaging PD will be “Pseudo PD”.

- Both clinical PD and radiation therapy are considered as PD, and no confirmation is required.

The best overall response for each subject across the time points is derived based on the rank CR > PR > SD > pseudo-PD > PD (including clinical PD, confirmed imaging PD, and radiation therapy) > NE.

For confirmed overall response for each visit, in addition to the rules listed above, the following rules should also be applied.

- If overall response of a visit is CR or PR, a confirmatory visit at least 4 weeks later is required. Overall response for the visit is derived based on overall response at the first time point and overall response at the confirmatory visit.
- If overall response of a visit is SD/NE, no confirmatory visit is required and the overall response for the visit is SD/NE correspondingly.

The rule for deriving confirmed overall response at each visit is specified in [Table 5](#). The best confirmed overall response for each subject across the time points is derived based on the rank CR confirmed > PR confirmed > CR not confirmed > PR not confirmed > SD > pseudo-PD > PD (including clinical PD, confirmed imaging PD, and radiation therapy) > NE.

Table 5. Confirmed Overall Response Derivation

Overall Response at First Visit	Overall Response at Confirmatory Visit	Overall Response for the Time Point	Date of Response
CR	CR	CR confirmed	First visit
	Responses other than CR or there is no confirmatory visit	CR not confirmed	First visit
PR	CR/PR	PR confirmed	First visit
	Responses other than CR/PR or there is no confirmatory visit	PR not confirmed	First visit
PD	PD/ clinical PD/ radiation therapy, or there is no confirmatory visit	PD	First visit
	NE	PD	First visit
	Responses other than PD/clinical PD/ radiation therapy/NE	pseudo-PD	First Visit
NE	Not required	NE	First visit
SD	Not required	SD	First visit

Note: Response after treatment discontinuation does not need to be confirmed.

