6.2.9. Disease and Response Assessment

6.2.9.1. Efficacy Measurement

RECIST version 1.1 [{Eisenhauer 2009}](#) [[Appendix 5](#)] will be used for assessment of tumor responses for the purposes of study evaluation, managing patients on protocol treatment, and decision making for discontinuation of study therapy due to disease progression, with some modifications to account for atypical responses which may occur with immune-based therapies [{Swaika 2015}](#). Given that anti PD-1 agents produce antitumor effects by potentiating endogenous cancer-specific immune responses, the response patterns seen with these agents may extend beyond the typical time course of responses seen with cytotoxic agents. In addition, anti-PD-1 therapies can occasionally manifest a clinical response after an initial increase in tumor burden or even the appearance of new lesions (“tumor flare” or “pseudoprogression”) [{Topalian 2014}](#). In these cases, standard RECIST may not provide an accurate response assessment of anti PD-1 agents.

Therefore, RECIST 1.1 will be used [[Appendix 5](#)] with the following adaptations:

If imaging shows a CR or PR, tumor imaging should be repeated at least 4 weeks (≥ 4 weeks) later to confirm response, per RECIST 1.1 guidelines. Subjects will then return to regular scheduled imaging every 8 weeks starting with the next protocol-specified imaging time-point. Subjects who obtain a confirmatory scan do not need to undergo scheduled imaging assessment ≤ 2 weeks later (eg, if a subject obtains a scan at Week 22 to confirm a Week 16 response, they will not also be required to complete the scheduled Week 24 scan).

If imaging shows progressive disease (PD), it is at the discretion of the investigator to keep the subject on study treatment or to stop study treatment until imaging is repeated ≥ 4 weeks later in order to confirm PD (adapted from the immune-related response criteria recommendations) [{Wolchok 2009}](#). Patients that are deemed clinically unstable or who have biopsy-proven new metastatic lesions are not required to have repeat imaging for confirmation. The decision to continue a subject on study while awaiting PD confirmation will be based on clinical judgment of a subject’s overall clinical condition, including performance status, clinical symptoms, and laboratory data.

At a minimum, subjects must meet the following criteria for continued treatment on study after disease progression is identified at a tumor assessment:

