- Absence of signs and symptoms (including worsening laboratory values) indicating disease progression
- No decline in ECOG performance status
- Absence of rapid progression of disease or of progressive disease at critical anatomical sites (eg, cord compression) requiring urgent alternative medical intervention

Study treatment may continue under the following circumstances after repeat/confirmatory imaging (≥ 4 weeks after initial scan showing PD):

- If repeat imaging shows $< 20\%$ tumor burden increase compared to nadir, stable or improved previous new lesion (if identified as cause for initial PD), and stable/improved non-target disease (if identified as cause for initial PD), treatment may be continued and/or resumed (PD is not confirmed).
- If repeat imaging confirms PD due to any of the scenarios listed below, subjects will be discontinued from study therapy with the following exception: if the subject is achieving a clinically meaningful benefit, and there is no further increase in the tumor burden at the confirmatory tumor imaging compared to the initial PD assessment, an exception to continue treatment may be considered following consultation with the Sponsor. In this case, if treatment is continued, tumor imaging should continue to be performed at the protocol specified intervals.

In determining whether or not the tumor burden has increased or decreased, site study team should consider all target lesions as well as non-target lesions.

If repeat imaging shows an objective response or stable disease relative to nadir, treatment with study medication may continue and subjects will return to regular scheduled imaging every 8 weeks starting with the next protocol-specified imaging time-point. Subjects who obtain a confirmatory scan do not need to undergo scheduled imaging assessment ≤ 2 weeks later (eg, if a subject obtains a scan at Week 14 to confirm a Week 8 PD and progression is not confirmed, they will not also be required to complete the scheduled Week 16 scan).

Progressive Disease is confirmed at repeat imaging if:

- Tumor burden remains $\geq 20\%$ (and at least 5 mm absolute increase) compared to nadir
- Non-target disease resulting in initial PD is worse (qualitative)
- New lesion(s) resulting in initial PD is worse (qualitative)
- Additional new lesion(s) since last evaluation

If repeat imaging confirms PD, subjects will be discontinued from study therapy.

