- a Day 1 visit must occur within 3 days following randomization.
- b Complete physical examination (PE) to be performed at Screening, EOT and EOS. A modified PE capturing changes from prior exams will be performed at subsequent visits. Height is required at Screening only.
- c ECOG performance status on Day 1 may be waived if has been conducted during screening within 4 days of Day 1.
- d Adverse events will be assessed and concomitant medications will be recorded at each clinic visit from Screening up to and including the 30-day Safety Follow-up visit or EOS visit whichever is later.
- e For Arm A: Study drug andecaliximab (800 mg) will be administered via IV infusion every 2 weeks over 30 (± 5) min. Nivolumab (3 mg/kg) will be administered via IV infusion following the completion of andecaliximab every 2 weeks over 60 (± 5) min. For Arm B: Nivolumab alone (3 mg/kg) will be administered via IV infusion every 2 weeks over 60 (± 5) min.
- f If applicable (females of child bearing potential). Serum pregnancy testing will be conducted at Screening. Urine pregnancy testing will be conducted pre-dose on Day 1 and then every 4 weeks, at EOT, and EOS, 30-day, and 5-month Safety Follow-up.
- g For Arm A only, plasma samples will be collected for andecaliximab PK at 30(± 15) min after the end of infusion on Day 1. For Weeks 4, 8, 16, and 24 and every 3 months thereafter, PK will be collected prior to dosing and 30(± 15) min after the end of infusion. It will also be collected at EOT and EOS.
- h For Arm A only, serum samples for anti-andecaliximab antibody will be collected prior to dosing on Day 1, Week 4, Week 8, Week 16, Week 24, and every 3 months thereafter, EOT and EOS.
- i Blood biomarkers will be collected at screening and prior to dosing on Day 1; Week 2; Week 4; Week 8; Week 16; Week 24 and every 3 months thereafter and at progression or EOS.
- j [REDACTED]
- k Tumor evaluation by CT or MRI will be performed during screening and approximately every 8 weeks regardless of visit week or dose interruption. Scan at EOS visit is not necessary if restaging scan is performed within the prior 8 weeks. Treatment response assessment will be per RECIST v1.1.

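### SAP 6.1 confirms progression on the repeat visit's response category alone, so a new lesion that persists without worsening can be scored as definitive PD where the protocol says PD is not confirmed

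*SAP*

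**What the plan says.** **Protocol 6.2.9.1** adapts RECIST 1.1 because "anti-PD-1 therapies can occasionally manifest a clinical response after an initial increase in tumor burden or even the appearance of new lesions". After a first PD, a repeat scan at least 4 weeks later decides whether PD is confirmed. Any one of four findings confirms it:

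- tumor burden still at least 20%, and at least 5 mm, over nadir;
- worse non-target disease, where that caused the first PD;
- for a first PD caused by a new lesion, "New lesion(s) resulting in initial PD is worse (qualitative";
- "Additional new lesion(s) since last evaluation".

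PD is not confirmed if burden is less than 20% over nadir and the finding that caused the first PD has not worsened. For a new lesion the condition is "stable or improved previous new lesion (if identified as cause for initial PD", and non-target disease has a parallel condition.

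**SAP 6.1** confirms a first imaging PD by several routes. The one at issue is "The overall response at the confirmatory visit is also PD". Table 5 allows pseudo-PD only when the repeat visit falls under "Responses other than PD/clinical PD/ radiation therapy/NE". Neither place mentions the cause of the first PD or whether it worsened, and SAP section 6 does not cite protocol 6.2.9.1.

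**Which criteria sites record.** Footnote k of protocol Appendix 2, repeated in SAP Appendix 2, says "Treatment response assessment will be per RECIST v1.1" and does not mention the modifications. Protocol 6.2.9.1, 6.2.9.2 and Table 6-2, and SAP 1.2, all refer to modified criteria.

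**The concern.** In the time-point table of protocol Appendix 5, a new lesion gives an overall response of PD whatever the target and non-target lesions do. If visits are scored that way, a new lesion that is still visible at the repeat scan makes the visit PD again, even if it is unchanged or smaller. The SAP then confirms the PD and the protocol does not.

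Three endpoints depend on the answer:

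- **PFS** (SAP 6.2.1): confirmed imaging PD is an event and pseudo-PD is not. Table 5 dates the PD to the first visit.
- **DOR** (SAP 6.2.3): the same definition ends the response of a subject who had already responded.
- **ORR** (SAP 6.1): assessments after confirmed PD are excluded, so a later response would not count.

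New lesions before a response are one of the flare patterns for which the protocol adopted its modifications.

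**Working it through.** **Step 1. Apply both rules to the same pairs of scans, with the SAP column using plain RECIST 1.1 visit scores.**

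| Cause of first PD | Repeat scan | Protocol 6.2.9.1 | SAP 6.1 / Table 5 | Agree? |
|---|---|---|---|---|
| Target growth | Back to <20% over nadir, no new lesion | Not confirmed | Pseudo-PD | Yes |
| Target growth | Still ≥20% and ≥5 mm over nadir | Confirmed | Confirmed | Yes |
| New lesion | Gone, burden <20% | Not confirmed | Pseudo-PD | Yes |
| New lesion | Worse, or further new lesions | Confirmed | Confirmed | Yes |
| New lesion | Persists, stable or smaller, burden <20% | Not confirmed | Confirmed | **No** |
| Non-target disease | Stable, burden <20%, visit still recorded as PD | Not confirmed | Confirmed | **No** |

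If the repeat visit is scored with the protocol's modifications, the last two rows are not PD and the rules agree in every row.

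**Step 2. Follow one subject in the fifth row.** Week 8: target lesions stable, one new node, so PD. Week 12: target lesions down 35%, node unchanged.

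- Protocol: burden is under 20% over nadir and the node is not worse, so PD is not confirmed.
- SAP with plain scoring: Week 12 is PD again, so there is a confirmed PD and a PFS event dated Week 8.
- Under the protocol's reading the subject is still without definitive progression at Week 12. The SAP event is therefore at least 4 weeks too early.

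**Step 3. See when ORR is affected.** While the node persists, plain scoring records PD at every visit, so there is no response for the exclusion rule to remove. A response is lost through that rule only if the node later disappears and a CR or PR is then recorded. The protocol does not say how response is scored while a new lesion persists without worsening. The effect on PFS and DOR is therefore firmer than the effect on ORR.

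**Step 4. Size.** The documents give no rate for such cases. As an assumption only, 3–8% of subjects gives 0.03 × 120 = 3.6 to 0.08 × 120 = 9.6 subjects. This is a ceiling for that assumption, because it takes every such visit to be scored by plain RECIST 1.1.

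**Step 5. What one lost responder would mean.** Inputs from protocol 3.2 and 8.10: 60 per arm, ORR 25% versus 45%, one-sided alpha 0.10, stated power about 83%. With Δ the difference, p̄ the mean rate and z = 1.2816:

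Power = Φ[(Δ − z·SE0)/SE1], where SE0 = √(2p̄(1 − p̄)/60) and SE1 = √((p1(1 − p1) + p2(1 − p2))/60).

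- As planned: SE0 = √(2 × 0.35 × 0.65/60) = 0.0871; SE1 = √((0.1875 + 0.2475)/60) = 0.0851; power = Φ(1.038) = 85.0%. Exact enumeration of the Mantel-Haenszel test with continuity correction gives 81.1%. The stated 83% lies between the two and is not in dispute.
- One responder fewer in Arm A only: p2 = 0.45 − 1/60 = 0.4333; SE0 = 0.0866; SE1 = 0.0850; power = Φ(0.852) = 80.3%.

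This illustrates sensitivity and is not a prediction. It matters for the formal test only if the primary-analysis SAP has the same rule. Which arm would lose responders is unknown.

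**The case against.** The strongest reply is that the conflict disappears if sites record the modified reading, and that most of the text points that way. Protocol 6.2.9.1 applies the adapted criteria to study evaluation. Section 6.2.9.2 evaluates tumor burden with those modifications. Table 6-2 refers to them for the repeat scan. Footnote q sends PD confirmation to section 6.2.9. SAP 1.2 mentions modifications, and SAP section 6 uses investigator assessments. On this view footnote k is shorthand in a schedule table.

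This stands as a limit: misclassification is possible but not shown. It does not remove the point. The SAP lists no modifications and never ties its confirmation test to 6.2.9.1, and footnote k appears without them in both documents. SAP 6.1 calls its criteria revised, but that does not decide the matter, because Appendix 5 uses the same word for the standard guideline. A programmer who follows SAP 6.1 and Table 5 literally on plain RECIST responses would depart from the protocol.

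A reader might infer that every tumor-flare subject is scored as definitive PD, or that the reported ORR and PFS are wrong. The documents support neither:

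- Target-lesion flare that regresses, and a new lesion that resolves by the repeat scan, are not confirmed PD under either document.
- SAP 1 and SAP 6 base CSR efficacy on the primary analysis under a separate SAP, which is not available here. P-values in this follow-up SAP are for display only.

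**Conclusion.** The point holds in limited form. SAP 6.1 and Table 5 state a confirmation test different from the one in protocol 6.2.9.1. The two give opposite answers for a new lesion that persists without worsening while burden is under 20% over nadir. They also differ for stable non-target disease that is still recorded as PD.

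The conflict is real only if the recorded visit response is plain RECIST 1.1, which the documents leave open. Where it is real, each affected subject gets a PFS event at least 4 weeks too early, and a prior responder also gets a DOR event. An ORR loss through the exclusion rule needs the further condition that the lesion later resolves and a response is recorded.

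The number affected is unknown; the 3.6 to 9.6 subjects rest on an assumed rate. No effect on the CSR efficacy results can be shown without the primary-analysis SAP. The ambiguity should still be removed, because it concerns the event definition for PFS and DOR and is cheap to settle.

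**What to change.** In SAP 6.1 and Table 5, define PD at the confirmatory visit by the four confirmation criteria of protocol 6.2.9.1, using the site's own confirmed or not-confirmed determination. Alternatively, declare that plain RECIST 1.1 is intended for the analysis and reconcile the SAP with the protocol. In either case, state which reading the recorded visit response represents and bring footnote k into line.

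Check the primary-analysis SAP for the same rule, since it governs the CSR efficacy results. A sensitivity analysis that counts the first RECIST 1.1 PD as the event is optional.

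The cost is minor SAP wording and programming, with no new scans. The site's confirmation judgment must be available in the data, and the documents do not show that it is recorded as a separate field. The change concerns endpoint derivation only and takes no position on continuing or stopping treatment.

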6.2. Secondary Efficacy Endpoint

6.2.1. Progression-Free Survival

Progression free survival (PFS), defined as the interval from the date of randomization to the earlier of the first definitive PD (as defined in Section 6.2.1) or death from any cause. The first definitive PD is defined as the first radiation therapy, the first clinical PD, and the first confirmed imaging PD, whichever comes first. Pseudo-PD will not be considered as definitive PD.

Data will be censored on the date of last adequate tumor assessment for subjects (including assessments with a NE outcome):

- who do not have definitive PD or die before study discontinuation, or
- who start new anticancer therapy prior (radiation therapy excluded) to definitive PD or death, or
- who have ≥ 2 consecutive missing tumor assessments before definitive PD or death.

Subjects without any adequate baseline tumor assessment are censored on the randomization date. The adequate baseline tumor assessment is defined as the window from (randomization date - 35 days) to randomization date.

PFS in months will be calculated as $(\text{date of event/censoring} - \text{date of randomization} + 1) / 30.4375$.

Survival function of PFS is estimated using Kaplan-Meier method and compared using the log-rank test stratified by PD-L1 status at screening. PFS rates at 1, 2, 3, 6, 9, 12 months, and the median with 95% CIs will be derived using Kaplan-Meier methods by treatment arm. Kaplan-Meier curves will also be provided. In addition, hazard ratio (HR) and corresponding 95% CI will be estimated for PFS using the Cox proportional hazards regression model stratified by PD-L1 status at screening.

Follow-up time in months for PFS will be summarized as a continuous variable with descriptive statistics.

- For a subject who is censored from PFS and has discontinued from tumor assessment, duration of PFS follow-up = $(\text{Date of Censoring} - \text{randomization date} + 1) / 30.4375$
- For subjects with a definitive PFS event and censored subject with ongoing tumor assessment, duration of PFS follow-up = $(\text{Date of last tumor assessment in the database} - \text{randomization date} + 1) / 30.4375$

For subjects who have imaging examinations on various dates that are nevertheless assigned to the same nominal visit, the following rules apply for the calculation of the endpoint date:

- The response date will be the last date associated with that particular imaging time point.

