6.2.3. Duration of Response

Duration of response (DOR) is defined for subjects in the ITT analysis set who are CR/PR prior to new anti-cancer therapy (including radiation therapy) as the interval from the date of the first objective response achieved to the earlier of the first definitive disease progression or death from any cause. The first definitive disease progression is defined in Section 6.2.1. The same censoring rules as for PFS will be applied to DOR.

DOR in months = (date of event/censoring – date of first response [CR or PR] + 1) / 30.4375.

Median DOR and 95% CIs will be estimated using Kaplan-Meier methods by treatment arm. Kaplan-Meier curves will also be provided.

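### SAP 6.1 gives two incompatible results for a first imaging PD followed by NE and then a further scan: pseudo-PD in the text, PD in Table 5

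*SAP*

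**What the plan says.** SAP 6.1 lists the cases in which a first imaging PD counts as confirmed. For a non-evaluable confirmatory visit the case is: "The overall response at the confirmatory visit is non-evaluable (NE) and no more tumor assessments follow the confirmatory visit". A separate case covers later clinical PD or radiation therapy. For anything not listed, the text says "Otherwise, the first imaging PD will be" pseudo-PD.

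The section then turns to confirmed response, which is the sensitivity analysis: "For confirmed overall response for each visit, in addition to the rules listed above, the following rules should also be applied". It adds: "The rule for deriving confirmed overall response at each visit is specified in" Table 5. In that table, a first-visit PD with NE at the confirmatory visit has its own row. The result is PD, dated at the first visit, with no condition on later scans. The pseudo-PD row is limited to "Responses other than PD/clinical PD/ radiation therapy/NE".

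Three other statements determine what follows from the classification:

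- SAP 6.1, on assessments left out of response: "or after confirmed progressive disease (PD) will not be included for ORR analysis".
- SAP 6.2.1, on PFS: "Pseudo-PD will not be considered as definitive PD". The section counts the first confirmed imaging PD as one form of definitive PD, but its cross-reference for definitive PD is to Section 6.2.1 itself.
- SAP 6.2.3, on DOR: "The first definitive disease progression is defined in Section 6.2.1".

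**The concern.** A programmer given the sequence PD, NE, then an evaluable scan finds two instructions in one section with opposite results. Under the text the first PD is set aside and later scans count. Under Table 5 it stands as PD at the first visit. The pseudo-PD row of the table expressly leaves NE out, so the table cannot return pseudo-PD after an NE, whereas the text can.

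At stake is whether a subject who responds after an apparent progression is counted as a confirmed responder. Late response after apparent progression is the pattern these rules exist to handle. Protocol 6.2.9.1 allows treatment to continue while PD is being confirmed, so scans after a first PD are expected. The trial is open-label and SAP 6 uses investigator assessments, so this choice should not be left to whoever programs the endpoint with the data in view.

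**Working it through.** The plan states no figure for this point, so there is none to reproduce. The check is to run the same scan sequences through both rules.

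**Rules as applied**

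- Text (SAP 6.1): first PD then NE is confirmed PD if no scan follows the NE, or if clinical PD or radiation therapy follows. Otherwise it is pseudo-PD.
- Table 5 (SAP 6.1): first PD then NE is PD at the first visit.
- Under either rule, scans after confirmed PD are dropped from response. Here Table 5's PD is treated as confirmed PD, a step taken up under the objection.

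**Sequences**, with scans every 8 weeks from Week 8 and the Week 16 scan serving as the confirmatory visit for Week 8:

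| Scans | Text | Table 5 |
|---|---|---|
| PD, NE, nothing after | PD at Week 8 | PD at Week 8 |
| PD, NE, PR, PR | pseudo-PD; best response confirmed PR; no PD | PD at Week 8; non-responder |
| PD, NE, SD, SD | pseudo-PD; best response SD; no PD | PD at Week 8 |
| PD, NE, PD, PD | read literally: pseudo-PD at Week 8, confirmed PD at Week 24 | PD at Week 8 |
| SD, PD, NE, SD | best response SD; no PD | best response SD; PD at Week 16 |

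The rules agree when nothing follows the NE. They disagree when a further scan follows and there is no subsequent clinical PD or radiation therapy. Of these five sequences, only PD, NE, PR, PR changes responder status. The others differ in the progression result, or not at all.

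**Size per subject, confirmed ORR.** Protocol 3.2 plans 60 subjects per arm, so one reclassified subject moves an arm's confirmed ORR by 1/60 = 1.7 percentage points.

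**Size per subject, PFS, only if Table 5 were carried into PFS.** For PD, NE, PR, PR, the text leaves the subject progression-free to at least Week 32, while Table 5 puts an event at Week 8. The gap is 32 − 8 = 24 weeks. With the SAP's divisor, 24 × 7 / 30.4375 = 168 / 30.4375 = 5.5 months.

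**Which endpoint uses which rule**

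- Primary (unconfirmed) ORR: the text only. Table 5 is introduced for confirmed response.
- Confirmed ORR: both, because the text rules are carried over and Table 5 is added.
- PFS and DOR: first confirmed imaging PD. The text defines confirmed PD as a term, and Table 5's result is labelled simply PD, so the text is the natural source. Section 6.2.1 does not say so.

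**The case against.** The strongest reply is that the two rules can be read together. Section 6.1 says its rules apply in the order listed, and Table 5 comes afterwards as a compact summary. On that view PD status is settled by the text before the table is used. The reply does not succeed. The ordering sentence introduces the text list and gives it no priority over the table. A table applied last would overwrite the earlier result. A mere summary would also have no reason to exclude NE from its pseudo-PD row.

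A second objection stands in part. Table 5's PD does not by itself cancel a later confirmed PR, because the ranking places confirmed PR above PD. The subject becomes a non-responder only if Table 5's PD counts as confirmed PD, so that later scans are excluded. The SAP does not state this. It is a plausible reading, because the ranking recognises imaging PD only as pseudo-PD or within a PD class described as including confirmed imaging PD. The conclusion is therefore worded conditionally.

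Three stronger readings are tempting, and the documents do not support them:

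- *The primary ORR is affected.* It is not, since Table 5 is confined to confirmed response.
- *PFS and DOR events move by months.* The 5.5-month gap arises only if Table 5 is used outside its stated scope. The self-reference in 6.2.1 leaves the source of the definition unstated but does not point to the table.
- *One reclassified subject could decide significance.* SAP 2.3 and 6 make these p-values display only. Formal testing and the efficacy results in the study report belong to a primary-analysis SAP that is not among the documents. The arithmetic also depends on the test. For 60 v 60 unstratified, moving from 15 v 21 to 15 v 22 responders takes the one-sided p from 0.117 to 0.084 asymptotically. An exact test gives 0.160 and 0.118, both above 0.10, and SAP 6.1.2 names an exact CMH method.

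**Conclusion.** The contradiction is real but limited. For a first imaging PD, then an NE confirmatory visit, then a further tumor assessment, with no subsequent clinical PD or radiation therapy, SAP 6.1 gives pseudo-PD in the text and PD in Table 5. The direct conflict lies in the confirmed-ORR sensitivity analysis, at 1.7 points per affected subject in an arm of 60. That size assumes a later confirmed response and that Table 5's PD is treated as confirmed PD. The same subject could then be a responder in the primary ORR and PD in its sensitivity analysis, for a reason unrelated to confirmation of the response.

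For PFS and DOR there is an unstated definition, most naturally resolved in favour of the text. The total effect cannot be computed, because the documents give no frequency for the sequence. No claim is made about the formal test.

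**What to change.** Three edits to the SAP:

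1. Split the Table 5 row for PD followed by NE. With no later tumor assessment, the result is PD. With a later tumor assessment and no subsequent clinical PD or radiation therapy, the result is pseudo-PD. Where clinical PD or radiation therapy does follow, it stays PD, as the text already provides.
2. In Section 6.2.1, replace the self-reference with a reference to the definition of confirmed PD in Section 6.1.
3. State that this single derivation feeds ORR, confirmed ORR, PFS and DOR.

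Classifying the first PD by the next evaluable scan would not reconcile the passages. For PD, NE, PD it would confirm the first PD, where the text read literally gives pseudo-PD, so it would be a third rule.

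The cost is one table row and one or two sentences, with no new data.
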